We propose to perform a prospective, randomized, double-blind placebo controlled trial. Patients will be included if they are: 1) receiving outpatient hemodialysis at the James J. Peters VAMC, 2) receiving IV vitamin D therapy according to National Kidney Foundation guidelines, 3) between the ages of 45-89 years, 4) a veteran outpatient or stable community living center patient, and 5) able to ambulate independently or with an assistive device for at least 20 feet. Exclusion criteria include: 1) 25-OH vitamin D level \geq 25 ng/ml, 2) hypercalcemia, 3) active malignancy within 6 months, 4) receiving intravenous antibiotics for infection, 5) history of dementia, 6) hemoglobin $<$ 8.5g, 7) history of conditions that interfere with postural instability (e.g. cerebellar disease, vestibular disease or any others that may present), and 8) poor compliance with dialysis treatments (history of skipping \geq 2 treatments per month for $>$ 2 months). A 25-OH vitamin D level of $<$ 25 ng/ml level was chosen based on previous studies that have shown that patients have the greatest improvement in muscle strength when levels below this threshold are increased. Patients will first be identified based on the inclusion criteria, then informed about the study and consented. Those who meet the exclusion criteria will be randomized to treatment or placebo. Enrolled participants will be randomized 2:1 to receive vitamin D (n=20) or placebo (n=10) for 6 months. All participants will be tested twice over two weeks to establish baseline values. Following baseline testing, the treatment group will receive 50,000 IU (standard replacement therapy) of oral cholecalciferol or placebo. The initial dose of cholecalciferol will be 50,000 IU weekly for 6 weeks. Vitamin D levels will then be measured. Participants who still have Vitamin D insufficiency (\leq 35 ng/ml) will remain on 50,000 IU of cholecalciferol for another 6 weeks, at which point Vitamin D levels will be measured again. Participants who reach 25-OH levels $>$ 35 ng/ml will have their dosing regimen lessened to 10,000 IU weekly (maintenance dose) for the remainder of the 6 months. Participants receiving placebo will start taking the placebo maintenance dose after the first 6 weeks. For safety monitoring, 25(OH) vitamin D₃ levels will also be re-measured at monthly intervals and followed by an independent medical monitor. In patients who have serum vitamin D levels \geq 60

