Mental Status: Mini-Mental Status Exam (MMSE) (for screening), Short Blessed Test (SBT)		X							X
Executive Function: Trails B, STROOP Color-Word		X							X
Memory: California Verbal Learning Test (CVLT-II)		X							X
Attention & Processing Speed: Trails A, DS WAIS-III, SDMT, StroopColor, Stroop Word		X							X
Language: Category Fluency, Controlled Oral Word Association Test		X							X
Metabolic & Endocrine Tests	X	X	X	X	X	X	X	X	X
Vitamin D Monthly Renal Clinic labs (chart review) B12 Folate		X	X		X	X	X	X	X
Immune Function Tests serum cytokines		X							X
Demographic Data & Health Monitoring									
Age, Height, Weight, BMI, Co-morbidities, HD Hx (chart review)		X							X

Power analysis: We expect that vitamin D supplementation will improve muscular function and strength. Using information from the limited studies reported in the literature, Pfeifer, et al. (25) reported an 11% decrease in the timed up and go test for individuals treated with Vitamin D replacement therapy compared with placebo who had an average decrease. We believe our study subjects will respond in a similar manner and have powered our study such that we expect 15 of 20 subjects in the treatment group to achieve an 11% decrease in the TUG test, consistent with the Pfeifer, et. al. study findings. Similarly, postural sway has been reported by two different groups to decrease by 9% (24) and 28% (25). To be conservative, we have chosen an expected 15% decrease in postural sway in our study subjects. Muscle strength as measured by hip extensor has been reported to improve by 16% (26), and by knee extensor strength gains from 8% to 25% (25, 26). Therefore to be on the conservative side, we have

hypothesized a 10% muscle strength increase in hand grip and hip flexor strength. Only 1 of 10 in the placebo-control group is anticipated to demonstrate these improvements.

We estimate power for a two-sided test using a continuity correction. At an alpha of 0.05, with treatment response of 75% and placebo response of 10%, we estimate 90% power for a sample size of 26; 80% power with a sample size of 22 and 70% power for a sample size of 18. We are proposing a sample of 30 permitting 33% drop out to permit us to maintain reasonable power for a pilot study.

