There is little information on the effect of vitamin D replacement therapy and change in cognitive function. Based on previous studies that demonstrated a correlation between poor performance and vitamin D deficiency, we expect vitamin D supplementation to improve SBT and MMSE scores (27, 30, 61). Of note, the cognitive function tests are our secondary outcome variables and we expect to gain empirical information after performing exploratory analyses regarding the effect of vitamin D replacement on cognitive function as part of this pilot study. A demonstration of improvement in neuromuscular and/or cognitive function would lead to the immediate implementation in clinical practice of 25-OH vitamin D supplementation in the care of HD patients who are vitamin D deficient and a future larger study to demonstrate dosing and length of time for maintenance of sufficient vitamin D levels to retain this positive effect.

Statistical Analysis Plan: Subjects will be randomized in a prospective, two-group, randomized study design utilizing a convenience sample of patients on hemodialysis. Subjects will be randomized to the treatment (Vit D) or placebo groups using a 2 to 1 block randomization determined from a web-based program (<http://www.randomization.com>). Subjects will be grouped in order of consenting such that the first 6 subjects will be in block 1, the next 6 in block 2, and so on. Five blocks will be performed. Each block will contain 6 subjects (2:1), with 4 subjects being randomized to vitamin D treatment to 2 subjects being randomized to the control group. Percent change scores will be calculated for both time points after treatment (3 or 6 month values – Baseline)/ Baseline * 100 for all primary outcome dependent variables (50ft timed walk, TUG, timed stair climb, Chair Raise, Functional Reach, postural sway, handgrip strength, and flexor/abduction strength) for each subject in both groups.

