The primary analysis for functional and cognitive outcomes will use the responder analysis described above. Additional secondary analyses will be performed on the primary outcome variables. In the first analysis, the percent change variables will be used for the group comparisons and analyzed by one-way analysis of variance (ANOVA) ($Y_1 = \%$ change; $X_1 = \text{Group}$). The percent change variable has the advantage of being easily analyzed in an analysis of covariance (ANCOVA) model if controlling variables are identified. For example, years on hemodialysis (HD y) may be need to be controlled for and as such this model would be $Y = \%$ change; $X_1(\text{HD y}) + X_2(\text{Group})$. The second analysis to be performed on the primary outcome variables will be the more traditional two-factor mixed model (2x3 table), where the between factor is Group (treatment, placebo) and the repeated measures (i.e. the within-subjects) factor is Time (BL, 3 and 6 months). In the case of missing data we will use 2 imputation methods. First as is commonly done in clinical trials of cognitive impairment and dementia we will use the last observation carried forward for missing terminal visits. We will compare results from these methods with a variety of other imputation methods. For missing data within a specific test, we will assign the average the remaining domains for those that do not complete a domain. Other imputations will include assigning values from 1) a regression across the available time points, and 2) assigning the average value of all subjects within in the group. We will compare results using these different imputations.

Significant main effects will further be explored by single degree of freedom post hoc analyses. For the secondary analyses covariates will be used including age and education adjusted T scores will be used for the baseline versus 6 month comparisons by performing a 2x2 repeated measures ANOVA. For

the self assessment variables (PASIPD and NIH PROMIS) percent change will be calculated as previously described and analyzed by one-way ANOVA as described for the primary outcome variables above.

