Blood draws for vitamin D and B12 Folate levels will require about 5 ml of blood for each draw. All Vitamin D levels will be determined by Quest Laboratories. B12 Folate levels will be determined by kit assay in [name] core laboratory as part of the CMCSCI. Vitamin D levels will be tested twice to establish baseline values. Vitamin D levels will be tested once a month during the treatment phase for safety monitoring. B12 Folate levels will be tested at baseline and 6 months. Blood draws for immune function tests will take place during dialysis sessions at baseline and 6 months. These tests will require a total of a 43cc draw. Immune function measurements include serum cytokines.

Chart review A chart review will be performed for all participants. The chart reviews will be performed by [name] (PI). No subject time commitment is required for the chart reviews.

3. Describe population to be studied, listing basis for selection or exclusion. Include number to be studied.

Individuals with advanced chronic kidney disease on hemodialysis (HD) will be studied. Thirty participants will be studied: 20 in the treatment group and 10 in the placebo group. Enrolled patients will be randomized into either the treatment or placebo group.

4. If subjects are patients, will conventional therapy or diagnostic procedures be withheld or modified for the purpose of this study?

If participants in this study are patients, conventional therapy or diagnostic procedures will not be withheld or modified. All participants will receive their normal care throughout their involvement in research.

b. List Possible RISKS

1. List possible hazards to subjects and/or investigative personnel from the procedures, drugs, or isotopes to be employed.

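### The stated power at reduced sample sizes (90/80/70% at 26/22/18) does not hold under the planned 2:1 allocation; the named method gives about 86/75/58%, although the full 30 still has about 93%

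*Combined protocol and SAP*

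**What the plan says.** The Power analysis paragraph (section C) sets out its method and inputs: "We estimate power for a two-sided test using a continuity correction", and "At an alpha of 0.05, with treatment response of 75% and placebo response of 10" per cent. From these, "we estimate 90% power for a sample size of 26; 80% power with a sample size of 22", with 70% quoted for 18. The paragraph then justifies the enrolment target: "We are proposing a sample of 30 permitting 33% drop out to permit us to maintain reasonable power for a pilot study".

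The allocation is given in three other places, always as 2:1. Research Design and Methods: "Enrolled participants will be randomized 2:1 to receive vitamin D (n=20) or placebo (n=10) for 6 months". Statistical Analysis Plan: "Each block will contain 6 subjects (2:1), with 4 subjects being randomized to vitamin D treatment", with the other 2 going to control. Basic Information, item 3: "Thirty participants will be studied: 20 in the treatment group and 10 in the placebo group". The power paragraph itself expects 15 responders among 20 treated and 1 among 10 on placebo, but it attaches no ratio to the totals of 26, 22 and 18.

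The Statistical Analysis Plan makes this comparison the main one: "The primary analysis for functional and cognitive outcomes will use the responder analysis described above". It does not name the test.

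**The concern.** For a fixed total, a 2:1 split usually gives less power than an equal split, because the smaller arm dominates the variance and enlarges the continuity correction. Here the stated powers look too high for arms as small as 12 and 6.

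The adequacy of 30 patients is not in question. The figures for 26, 22 and 18 are, however, the only numerical support for the statement that a third of the patients can be lost with reasonable power remaining. If they do not describe the 2:1 design, the protection against drop-out is overstated for the primary responder analysis.

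**Working it through.** **Inputs.** Response 0.75 (vitamin D) and 0.10 (placebo), difference 0.65; two-sided alpha 0.05 (z = 1.96); continuity correction. All are from the Power analysis paragraph. The 2:1 ratio is from the sections listed above.

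**Formula.** With nT and nC patients and pooled rate p = (0.75·nT + 0.10·nC)/(nT + nC):

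- SE0 = √[p(1−p)(1/nT + 1/nC)]
- SE1 = √[0.75·0.25/nT + 0.10·0.90/nC]
- correction c = ½(1/nT + 1/nC)
- power = Φ[(0.65 − c − 1.96·SE0)/SE1]

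Inverting the Fleiss continuity-corrected sample size formula gives the same powers.

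**Step 1: reproduce the plan's figures.** Equal allocation comes close. At 13:13, p = 0.425, c = 0.0769, SE0 = 0.1939 and SE1 = 0.1461, so z = (0.65 − 0.0769 − 0.3800)/0.1461 = 1.32 and power is 90.7%. At 11:11 it is 82.1% and at 9:9 it is 68.0%. The unrounded totals required at 1:1 for 90/80/70% are 25.6, 21.3 and 18.5, against the stated 26, 22 and 18.

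**Step 2: the same method at 2:1.** At 12:6, p = 0.5333, c = 0.125, SE0 = 0.2494 and SE1 = 0.1750, so z = (0.65 − 0.125 − 0.4888)/0.1750 = 0.21 and power is 58.2%. At 20:10, c = 0.075, SE0 = 0.1932 and SE1 = 0.1356, so z = (0.65 − 0.075 − 0.3787)/0.1356 = 1.45 and power is 92.6%.

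| Total | Stated | 1:1 | Exactly 2:1 | Stated minus 2:1 |
|---|---|---|---|---|
| 30 | not given | 95.4% | 92.6% | – |
| 26 | 90% | 90.7% | 85.9% | 4.1 points |
| 22 | 80% | 82.1% | 74.7% | 5.3 points |
| 20 | not given | 75.8% | 67.1% | – |
| 18 | 70% | 68.0% | 58.2% | 11.8 points |

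The unrounded totals required at 2:1 are 28.2, 23.7 and 20.7 for 90/80/70%. In whole 2:1 sets these become 30, 24 and 21.

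**Step 3: whole-patient splits and the choice of test.** The two exact columns come from full enumeration of the binomial outcomes.

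| Split | Formula | Exact, continuity-corrected chi-square | Exact, Fisher |
|---|---|---|---|
| 20:10 | 92.6% | 92.1% | 92.7% |
| 17:9 | 86.7% | 84.7% | 91.7% |
| 18:8 | 83.8% | 83.9% | 90.2% |
| 16:8 | 81.0% | 80.4% | 88.0% |
| 14:8 | 77.3% | 77.9% | 84.7% |
| 15:7 | 73.2% | 73.8% | 75.7% |
| 14:7 | 71.1% | 77.3% | 78.6% |
| 13:7 | 68.8% | 69.9% | 72.8% |
| 14:6 | 62.9% | 66.7% | 80.2% |
| 12:6 | 58.2% | 60.2% | 74.8% |

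Enumeration of the continuity-corrected test confirms the shortfall at 26, 22 and 18, so it is not an artefact of the normal approximation.

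**Step 4: the drop-out allowance.** A third of 30 is 10 losses, leaving 20 evaluable. The stated figures place 20 between 70% (at 18) and 80% (at 22). Near 2:1, the named method gives 68.8% (13:7) or 62.9% (14:6).

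**Step 5: other readings at 2:1.** None restores the stated set at 26/22/18. Dropping the correction gives 95/91/82%, a one-sided test with the correction gives 94/87/74%, and unweighted pooling gives 87/76/59%.

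**The case against.** The strongest reply is that little depends on this. The trial is a pilot, the full sample has about 93% power, and the plan promises only reasonable power after losses, not 80%. That is fair and limits the weight of the point, but numerical power claims should still match the design they describe.

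Second, 20 evaluable is a pessimistic case. The primary outcomes are also measured at month 3, and the Statistical Analysis Plan carries the last observation forward for missing terminal visits, so some drop-outs may stay in the analysis. Losses also need not preserve 2:1: a 12:8 split gives 72.6% by the formula. Both points stand as qualifications. Near 2:1 remains the natural planning assumption, and the plan does not say whether its allowance counts carried-forward patients.

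Third, the result depends on the test. With Fisher's exact test near 2:1, power is 90-92% at 26 and 75% at 18, meeting or exceeding the stated values. At 22 it is 84.7% (14:8) or 75.7% (15:7), so even Fisher's test can fall below the stated 80%. The plan's power paragraph specifies a continuity-corrected test, which is the basis for the comparison here.

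Finally, discreteness moves exact power by several points between neighbouring splits, which is comparable to the gaps at 26 and 22. Only the 12-point gap at 18 is clearly larger. But the formula and the exact continuity-corrected test both fall below the stated figure at all three sizes.

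**Conclusion.** The concern holds. With the plan's own response rates, alpha and continuity-corrected method, 2:1 allocation gives about 86%, 75% and 58% at 26, 22 and 18, not 90%, 80% and 70%. Power with 20 evaluable patients near 2:1 is 63-69% by the formula and 67-70% by exact enumeration of that test, so at or below the lowest power the plan quotes. The enrolment target is unaffected: 20:10 gives 92.6%.

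These results assume 75% and 10% response, a split close to 2:1 among evaluable patients and, for the figure at 20, that no drop-out is retained through carried-forward values. That the original calculation used equal arms is an inference from the close fit, and the fit is imperfect at 18 (68.0% against 70%).

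**What to change.** Keep 30 patients. State the 2:1 ratio in the Power analysis paragraph, name the test for the responder analysis in the Statistical Analysis Plan, and quote power for that ratio and test:

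- **If the continuity-corrected test is kept:** with 2:1 allocation, power is 93% at 20:10, 84-87% at 26, 73-77% at 22, 63-69% at 20 and 58% at 18. By the formula, 24 evaluable patients (16:8) are needed for 80% and 21 (14:7) for 70%.
- **If Fisher's exact test is chosen:** 93% at 20:10, 90-92% at 26, 76-85% at 22, 73-80% at 20 and 75% at 18.

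A shorter version giving only the ratio, the test, and power at 30 and at 20 would also do. In either case, restate the power left after 33% drop-out and say whether it counts patients kept in by last observation carried forward.

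The cost is wording in the protocol and SAP, with no extra patients. If the continuity-corrected test is kept, the quoted power at reduced sizes becomes less favourable.

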care of receiving active 1,25 OH vitamin D during dialysis. However, our objective is to supplement deficient 25-OH vitamin D levels with cholecalciferol (not active vitamin D, but substrate) which is currently not standard of care. Vitamin D supplementation will be administered in the unit by research staff to insure compliance. Administration of 50,000 units of cholecalciferol twice a month is the recommended dose to maintain 25-OH levels between 30 and 40 ng/mL in patients with advanced renal disease not yet receiving hemodialysis.

The management of secondary hyperparathyroidism of end-stage renal disease will be managed by the patient's nephrologists according to the NKF KDOQI guidelines. Active vitamin D analogs and a combination of calcium and/or non-calcium containing oral phosphate binders will be administered and titrated based on monthly routine dialysis laboratory tests in order to meet the recommended KDOQI targets for intact PTH, calcium level, and phosphorus level. In previous studies, administration of oral 25-OH vitamin D has not shown significant clinical effect on serum phosphorus or calcium levels.

The 25-OH vitamin D levels will be measured monthly and pre-dialysis blood-work will be evaluated monthly as part of routine clinical practice for serum calcium, albumin, phosphorus, and intact PTH. All patients will be receiving 3 hemodialysis sessions per week, 3 to 4 hours session based on achieved clearances, and standard calcium bath concentration of 1.5 mmol/L will be used.

C) PROCEDURES, METHODS AND EXPERIMENTAL DESIGN.

If this study involves human subjects, or biologic materials obtained from humans, sufficient information must be provided to weigh the risk against the benefits. The "Procedures" Section (IIC) should contain a detailed description of experimental design, methods and procedures.

Research Design and Methods:

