ng/ml, the frequency of administration will be reduced to once a month. The participants will receive supplementation for a total of 6 months. At this time, vitamin D levels will be reassessed and participants will undergo follow-up functional assessments, and cognitive and immune testing. Subjects will be recruited from the outpatient hemodialysis (HD) unit which is located on the fourth floor of the James J. Peters VAMC.

Primary Outcomes (tested at Baseline, 3 months and 6 months):

- 1) Neuromuscular functional performance using the 50ft timed walk, the TUG, a timed stair climb, and the Chair Raise test, (48)
- 2) Postural stability using a Sway meter (NeuroCom International, Inc., Clackamas, OR) that measures displacement of the body at the level of the waist in 30 second periods (49) and the Functional Reach test.
- 3) Muscle hand grip strength using the Harpenden Hand Grip dynamometer (50) and hip flexor and knee extensor strength using a Push-Pull Muscle Strength dynamometer.

Secondary Outcomes:

- 1) Cognitive function (tested at Baseline, 3 and 6 months):
 - a) Mental Status: Mini-Mental Status Exam (MMSE) (51) and Short Blessed Test (SBT) (52);
 - b) Memory: California Verbal Learning Test – II (CVLT-II) (53);
 - c) Language: Category Fluency and Controlled Oral Word Association Test (COWAT) (54);
 - d) Attention and Processing Speed: Trails A (55), Digit Span (56), Symbol Digit Modality Test (SDMT) (57), and Stroop Color and Word (58)
 - e) Executive Function: Trails B (55) and Stroop Color-Word (58).
- 2) Self-assessment of Physical Fxn and Health (tested at Baseline, 3 months and 6 months):
 - a) Physical Activity Scale for Persons with Physical Disabilities (PASIPD) (59)
 - b) NIH PROMIS (v1.0 Item Banks): Global Health Physical Function, Pain, Fatigue, Sleep, Emotional Distress (60)
 - c) Beck Depression Inventory (BDI)
- 3) Immunology (tested at Baseline, 6 months)
 - a) Serum cytokines

This study will be performed over two years.

TABLE 1. Study Flow Sheet	BL 1	BL 2	Month 1	6 weeks	Month 2	Month 3	Month 4	Month 5	Month 6
Week:	0	0 ₂	4	6	8	12	16	20	24
Physical Function Assessment 50ft walk, TUG, stair climb, Chair Raise, Functional Reach, Sway, Hand Grip, Hip & Knee Strength		X				X			X
Self - Assessment PASIPD & NIH PROMIS (short forms): Physical Fxn, Pain, Fatigue, Global Health, Sleep, Emotional Distress, BDI		X				X			X
Cognitive Impairment Tests									

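### The fixed 4:2 blocks of six, stated in the protocol, leave a small route to predicting allocations if masking leaks; varied, undisclosed block sizes would largely close it at little cost

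*Combined protocol and SAP*

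**What the plan says.** The Research Design and Methods part of Section C sets the ratio and totals: "Enrolled participants will be randomized 2:1 to receive vitamin D (n=20) or placebo (n=10) for 6 months". The Statistical Analysis Plan describes the list as produced "using a 2 to 1 block randomization determined from a web-based program". It then gives the block structure in full. Filling is sequential: "Subjects will be grouped in order of consenting such that the first 6 subjects will be in block 1, the next 6 in block 2," with later blocks filled the same way, up to a total of five. The make-up of every block is also fixed: "Each block will contain 6 subjects (2:1), with 4 subjects being randomized to vitamin D treatment to 2 subjects being randomized to the control group". There is one recruitment source: "Subjects will be recruited from the outpatient hemodialysis (HD) unit which is located on the fourth floor of the James J. Peters VAMC".

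Section B (Dosing of 25-OH vitamin D in HD Patients) says who gives the product: "Vitamin D supplementation will be administered in the unit by research staff to insure compliance". Under Research Design and Methods, every placebo participant moves to the placebo maintenance dose after week 6. Vitamin D participants at or below 35 ng/ml at that point stay on the loading dose, and those above it step down. At levels of 60 ng/ml or more, "the frequency of administration will be reduced to once a month".

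The plan also has safeguards. The trial is declared double-blind, an independent medical monitor follows the monthly 25-OH levels, and the principal investigator is to remain blinded. The documents do not describe varied block sizes, who holds the list, how the next allocation is concealed, or how the arm-dependent dosing is masked from the staff who give it.

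**The concern.** When the block size is fixed and known and blocks are filled in sequence, anyone who has worked out the earlier arms in a block can sometimes deduce the next one. Once both placebo places or all four vitamin D places are used, the rest of the block is determined. The choice to approach or consent a particular patient could then depend on the arm that patient would receive.

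This is selection bias at entry. It is a different route from knowing a participant's arm during follow-up. With 10 placebo participants, one selectively enrolled patient can move the placebo response rate by 10 percentage points, and the responder analysis has no stated covariate adjustment. The possibility of a leak is not fanciful, because the dosing rule can show a different pattern by arm and unit research staff carry it out.

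**Working it through.** **Inputs.** From the Statistical Analysis Plan: block of 6 (4 vitamin D, 2 placebo), 5 blocks, filled by order of consent. From Research Design and Methods: two-year study, 6 months of treatment, two weeks of baseline testing, first on-treatment 25-OH check at week 4, dose step at week 6. Enrolment pace is not given, so it is assumed below.

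**The plan's totals.** 5 × 6 = 30; 5 × 4 = 20; 5 × 2 = 10. These agree with the stated 20:10. The documents give no predictability figure.

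**Ceiling: every earlier arm in the block known at each consent.** A 4:2 block has C(6,2) = 15 equally likely orders. The number of places already determined is the length of the final run after one arm is used up: 1 in 8 orders, 2 in 4 orders, 3 in 2 orders and 4 in 1 order. The mean is (8×1 + 4×2 + 2×3 + 1×4)/15 = 26/15 = 1.733. The closed form agrees: 4/(2+1) + 2/(4+1) = 1.333 + 0.400. So 1.733/6 = 28.9%, and 5 × 1.733 = 8.67 of 30. Of these, 1.333 per block are vitamin D places, which become certain only once both placebo places are recognised. The other 0.400 are placebo places, certain once all four vitamin D places are recognised.

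**Delay before an arm can be recognised.** If the latest L participants are still masked at the next consent, each final run shortens by L, to a minimum of zero.

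| L | Mean per block | Share | Of 30 |
|---|---|---|---|
| 0 | 26/15 | 28.9% | 8.67 |
| 1 | 11/15 | 12.2% | 3.67 |
| 2 | 4/15 | 4.4% | 1.33 |
| 3 | 1/15 | 1.1% | 0.33 |
| 4 or more | 0 | 0% | 0 |

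**Which L is plausible.** Two years less 6 months of treatment leaves at most about 18 months to enrol. Taking 18 months (assumption), 18 × 30.4 / 30 is about 18 days per consent. Two weeks of baseline plus the week-4 check or the week-6 step gives 6 to 8 weeks, or 42 to 56 days, before an arm could show. 42/18 = 2.3 and 56/18 = 3.1, so L is 2 or 3, which gives 0.3 to 1.3 of 30. Faster enrolment raises L and lowers the figure.

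**Which arm the schedule reveals.** Staying on the loading dose after week 6, or moving to monthly dosing at 60 ng/ml or more, points to vitamin D. Stepping down at week 6 does not identify placebo, because vitamin D participants above 35 ng/ml also step down. If only vitamin D can be recognised, just the 0.400 component remains: 5 × 0.400 = 2.0 of 30 (6.7%) with no delay. With L of 2 or more it is zero, because at the sixth consent at most three earlier arms are visible and four are needed.

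**The case against.** The strongest case against is that the trial is declared double-blind, the investigator stays blinded, and levels go to an independent monitor. If that holds, nothing is predictable whatever the block size. The root gap would then be the unstated masking of arm-dependent dosing, and mending that would remove this point. Fixed blocks also have a merit in a pilot that might stop early, since they restore 2:1 after every six patients.

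Much of this stands. A reader might infer from the block structure that staff will know about 29% of allocations in advance. The documents do not support that. It would require both arms to be recognised immediately, whereas the schedule signals point only to vitamin D and appear weeks after consent. Nor do the documents say who at the unit reads the protocol, that staff know the patients personally, that the staff who dose also recruit, or how fast enrolment will run. It is also not enough that early members of a block are well into dosing before the block fills, because certainty depends on the most recent members.

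What does not stand is the step from this to leaving the design alone. The protocol states the exact block composition and describes no concealment step and no masking of the dose changes. Varied block sizes protect entry even if the dosing mask turns out to be imperfect.

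**Conclusion.** The point holds as a conditional and small one. A fixed, stated 4:2 block filled in order of consent, combined with arm-dependent dosing given by unit research staff, creates an avoidable route to foreknowledge. Its size depends on how far masking leaks:

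- At most 28.9% (8.7 of 30), if every earlier arm in the block is known at each consent.
- About 1% to 4% (0.3 to 1.3 of 30), if both arms become recognisable only after 6 to 8 weeks and enrolment takes 18 months (assumption).
- Zero, if blinding holds or if only vitamin D participants are recognisable with that delay.

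The ceiling should not be read as an expected value. The documents do not show that any allocation would in fact be known. The change is worth making because it is cheap.

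**What to change.** Keep 2:1 and 20:10. Before enrolment, generate a new list with randomly ordered blocks of varied sizes that are multiples of 3 and sum to 30, for example 6, 9 and 15. Have it held by someone not involved in recruiting or dosing, and say so in the protocol. Move block sizes out of the text that recruiting and dosing staff read. Separately, state how the arm-dependent dose changes are masked from the staff who give them; no dosing rule needs to change for this.

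Even if the sizes and order of 6, 9 and 15 leaked, the ceiling would be (4/3 + 2/5) + (6/4 + 3/7) + (10/6 + 5/11) = 1.73 + 1.93 + 2.12 = 5.78 of 30 (19%), below the present 8.67.

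The cost is one new list, a few sentences, and slightly looser balance over calendar time or if enrolment stops early. Suppose it stopped at 15 (assumption). The present blocks guarantee at least 4 placebo participants. With 6, 9 and 15 in random order, 3 or fewer placebo can occur only in the orders 6-15-9 (235/5005) and 9-15-6 (210/5005). Over the six orders that is (235 + 210)/(6 × 5005) = 1.5%. A single unblocked 20:10 list should not be used: its ceiling is lower (20/11 + 10/21 = 2.29 of 30), but its chance of 3 or fewer placebo at 15 is 12% (hypergeometric, 15 drawn from 20 and 10).
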